2.3.4.1.2 Risks related to study treatment

SAR444245 has the potential to induce CRS which could exacerbate the manifestations of COVID-19 infection. It is, however, worth noting that pegylated IL-2 bempegaldesleukin is currently being evaluated for the treatment of patients with mild COVID-19 in a Phase 1b study (NCT04646044).

2.3.4.1.3 Risks related to study related activity

It is important to minimize the risk of exposure of patients to COVID-19. In addition to the contingency measures described in [Section 10.9](#), the following prevention and mitigation plans could be implemented at clinical sites:

- All participating sites should have implemented measures according to regional/local Health Authorities, European Medicines Agency (EMA), ESMO, ASCO guidelines including but not limited to restrictions of access to the hospitals for visitors, physical distancing and personal protective equipment (PPE).
- Study participants should be treated in a dedicated area that is separated from patients with COVID-19 infection.

2.3.4.1.4 Conclusion on the benefit-risk assessment pertaining to COVID-19

Overall, the benefit-risk ratio is deemed acceptable in patients with relapsed or refractory B cell lymphoma during COVID-19 pandemic. The Sponsor will continue to evaluate the benefit-risk ratio during the study period.

3 OBJECTIVES AND ENDPOINTS

Table 1 - Objectives and endpoints

Objectives	Endpoints
Primary	

 To determine the antitumor activity of SAR444245 with or without other anticancer therapies. 	
 Refer to individual substudy.
Secondary	

 To confirm the dose and to assess the safety profile of SAR444245 when combined with or without other anticancer therapies. To assess other indicators of antitumor activity. To assess the plasma concentrations of SAR444245 when given with or without other anticancer therapies. To assess the immunogenicity of SAR444245. 	
 Incidence of treatment emergent adverse events (TEAEs), dose-limiting toxicities (DLTs), serious adverse events (SAEs), laboratory abnormalities according to National Cancer Institute Common Terminology Criteria for Adverse Events (NCI CTCAE) V5.0 and American Society for Transplantation and Cellular Therapy (ASTCT) consensus gradings (1). Time to response (TTR) defined as the time from the first administration of investigational medicinal product (IMP) to the first documented evidence of PR or CR determined by Investigator per Lugano response criteria 2014 (2). Duration of response (DoR) defined as the time from first documented evidence of PR or CR until progressive disease (PD) determined by Investigator per Lugano response criteria 2014 (2), or death from any cause, whichever occurs first. Clinical benefit rate (CBR) including CR or PR at any time or stable disease (SD) of at least 6 months (determined by Investigator per Lugano response criteria 2014) (2). Progression free survival (PFS) defined as the time from the date of first IMP administration to the date of the first documented disease progression determined by Investigator per Lugano response criteria 2014 (2) or death due to any cause, whichever occurs first. Plasma concentrations of SAR444245. Incidence of anti-drug antibodies (ADAs) against SAR444245.
Exploratory	

3.1 APPROPRIATENESS OF MEASUREMENTS

Each of the efficacy and safety assessments chosen for use in this study is considered well established and relevant in an oncology study setting.

In addition, suitable steps have been built into each of these assessments to ensure their reliability and accuracy and to minimize any risks to participant safety.

4 STUDY DESIGN

4.1 OVERALL DESIGN

This is a Phase 2, multi-cohort, un-controlled, non-randomized, open-label, multi-center study assessing the antitumor activity and safety of SAR444245 with or without other anticancer therapies in adults and adolescents with relapsed or refractory B cell lymphoma.

This study is developed as a master protocol in order to accelerate the investigation of SAR444245 with or without other anticancer therapies by identifying early signals. This design is with the flexibility to open new treatment cohorts as new treatment become available and close existing treatment cohorts that demonstrate minimal clinical activity or unacceptable toxicity.

The information that is introductory and common to all cohorts is included in the present document (“Master Protocol”), and cohort-specific elements are included in separate substudies. This study is designed with the flexibility to open new treatment arms or add new indications as permitted by scientific rationale.

A graphical presentation of the study schema is shown in [Figure 1](#).

A safety run-in will confirm the dose of SAR444245 in each substudy. Participants who fulfill the eligibility criteria of any cohort may be enrolled to the safety run-in of that cohort. After a maximum of 10 participants have been enrolled into a specific cohort, enrollment will be paused for that cohort.

Once a total of at least 6 participants are evaluable for DLT in a specific cohort, safety data for these participants will be reviewed by the Study Board. DLT-evaluable participants include all treated participants in the safety run-in part who have been observed for the DLT observation period (defined in the individual substudy). Any participant who experienced a DLT at any time during the DLT observation period will also be DLT-evaluable.

If after recruiting the first 10 participants there are fewer than 6 participants evaluable for DLT, more participants will be enrolled to ensure at least 6 DLT evaluable participants after agreement from SB. Participants who are enrolled in the safety run-in and treated at the confirmed safe dose will be included in the total number of participants for that specific cohort (for example, if 10 Cohort A participants are enrolled in the safety run-in, and treated at the confirmed safe dose, approximately 15 additional participants will be enrolled into Cohort A to have the total number of 25 participants).

The SAR444245 dose to be confirmed is 24 µg/kg, administered as an IV infusion over 30 minutes during each cycle (see [Section 1.1](#) Study interventions for details). Overall safety monitoring will be performed throughout the study. If recommended by the Study Board, SAR444245 dose may be reduced to █ µg/kg or another lower dose level which will be explored following the same process described in the safety run-in for 24 µg/kg dose level.

The Modified Toxicity Probability Interval 2 (mTPI2) design will be used in the safety run-in part. The mTPI2 design is a Bayesian interval design that can be implemented in a simple fashion as the traditional 3+3 design, but it is more flexible and possesses superior operating characteristics. The target toxicity rate for the MTD is 0.3, with the acceptable toxicity probability interval of (0.25,0.35). The dose decision (stay at 24 µg/kg dose or reduce the dose) will be made by the Study Board and will be guided by the decision rules from the mTPI2 design. The mTPI2 decision rules are based on calculating the unit probability mass (UPM) of intervals as following: (0, 0.05), (0.05, 0.15), (0.15, 0.25), (0.25, 0.35), (0.35, 0.45) (0.85, 0.95), (0.95, 1). In mTPI2 method, intervals that are lower than 0.25 indicate dose escalation, equivalence interval (0.25,0.35) indicates staying at the current dose level, and intervals that are higher than 0.35 indicate dose de-escalation. The interval with the largest UPM is the winning interval and implies the corresponding dose escalation/de-escalation decision. For the safety run-in part of the study, mTPI2 rules (see [Table 2](#)) will be applied as follows, unless decided otherwise by the Study Board:

- If the dose recommendation from mTPI2 is “E” (Escalate to the next higher dose) or “S” (Stay at the same dose), all cohorts treated at the current regimen will continue with the SAR444245 24 µg/kg dose
- If the dose recommendation from mTPI2 is to de-escalate to a lower dose (either “D” [De-escalate to the previous lower dose] or “DU” [De-escalate to the previous lower dose and the current dose will never be used again in the trial]), a dose lower than 24 µg/kg will be tested and assessed with the same methodology.

Table 2 - Dose escalation rule of the modified toxicity probability interval-2 method

		Number of DLT-evaluable participants									
		1	2	3	4	5	6	7	8	9	10
Number of dose limiting toxicities	0	E	E	E	E	E	E	E	E	E	E
	1	D	D	S	S	E	E	E	E	E	E
	2		DU	D	D	D	S	S	S	E	E
	3			DU	DU	D	D	D	D	S	S
	4				DU	DU	DU	D	D	D	D
	5					DU	DU	DU	DU	DU	D
	6						DU	DU	DU	DU	DU
	7							DU	DU	DU	DU
	8								DU	DU	DU
	9									DU	DU
	10										DU

E: Escalate to the next higher dose, S: Stay at the current dose, D: De-escalate to the previous lower dose, DU: De-escalate to the previous lower dose and the current dose will never be used again because of unacceptable high toxicity.

Note: a total of at least 6 participants are evaluable for DLT in a specific cohort, safety data for these participants will be reviewed by the Study Board to determine if the dose needs to be reduced.

Dose limiting toxicity: Selected events occurring during the DLT observation period (defined in the individual substudy) are considered as DLT unless due to disease progression or to a cause obviously unrelated to SAR444245. Please refer to the full list of events as below. Based on the occurrence of DLT and overall assessment of safety data supplemented with data from other SAR444245 studies, the Study Board will determine if the dose of SAR444245 needs to be reduced to █ μg/kg or another lower dose level, in agreement with the Sponsor.

Hematologic abnormalities:

- Grade 4 neutropenic fever (temperature $\geq 38.5^{\circ}\text{C}$ on more than 1 occasion).
- Grade 4 thrombocytopenia associated with clinically significant bleeding requiring clinical intervention.

Non-hematologic abnormalities:

- Grade 3 or above alanine aminotransferase (ALT) or aspartate aminotransferase (AST) in combination with a bilirubin $> 2 \times$ upper limit of normal (ULN) with no evidence of cholestasis or another cause, such as viral infection or other drugs.
- Grade 3 or above vascular leak syndrome (VLS)
- Grade 3 or above hypotension

- Grade 3 or above cytokine release syndrome
- Grade 3 or above AE that does not resolve to grade ≤ 2 within 7 days of starting accepted standard of care medical management.
- The following non-hematologic AEs are exceptions that are not considered DLTs:
 - Grade 3 or 4 laboratory abnormalities that are not clinically significant per recruiting Investigator and Sponsor will not be considered a DLT.

Study Board

The study Investigators (or designee) participating in the safety run-in of applicable cohorts and the Sponsor clinical team members will constitute the Study Board (SB). The SB will review clinical data on a regular basis. In order to decide dose confirmation or dose reduction on the basis of their knowledge of the safety data. Minutes of each meeting will be written by the Sponsor and distributed to all sites participating in the safety run-in. Decisions regarding final dose selection will be made during one of the SB meetings and documented in the meeting minutes.

After safety run-in dose confirmation, occurrence of any treatment related G3 or higher AE (excluding lymphocyte count decrease) not resolving within 72 hours in $>25\%$ of participants per regimen will trigger an ad hoc Data Monitoring Committee (DMC) to rapidly convene to assess safety or need to pause enrollment to allow for a safety review. The SB (during safety run-in), independent DMC (during core phase and expansion) and Sponsor can decide to stop any cohort in the event excessive toxicity (for example but not limited to excessive irAE or excessive number of G4/5 events) is observed.

Special considerations pertaining to methodology

Interactive Response Technology will be used to control recruitment, assignment per site and facilitate the handling, management, and accountability of drug supply.

The duration of the study for a participant will include:

- **Screening period:** Up to 28 days.
- **Treatment Period:** Enrolled participants will receive continuous treatment until PD, unacceptable adverse event (AE), or other full permanent discontinuation criteria as described in [Section 7](#), or completion of the maximum cycles allowed in the substudies. However, treatment beyond PD may be allowed for up to 9 weeks if the participant appears to be benefiting clinically after discussion with the Sponsor.
- **End of Treatment and Follow-up:** End of Treatment Visit will occur 30 days ± 7 days from last IMP administration or prior to initiation of further therapy. Participants will then enter the **Observation period** and will be followed differently depending on the reason leading to **End of Treatment (EOT)**:
 1. Participants who discontinue study treatment **without PD** or who **complete** the maximum cycles allowed in the substudies **without PD** (per Lugano response criteria 2014[2]), will be followed every 3 months ± 7 days from last IMP administration, for

safety (as per Schedule of Activities [SoA] in the individual substudy) and tumor imaging assessments, until PD, start of another anticancer therapy, final cohort cut-off, whichever comes first, before moving to the Survival Phone Call Follow-Up Period.

2. Participants who discontinue study treatment **with PD** (per Lugano response criteria 2014[2]) will be followed for safety in the Follow-Up Visit 1 occurring 3 months ± 7 days from last IMP administration, before moving to the Survival Phone Call Follow-Up Period.

Participants who move into the **Survival Phone Call Follow-up Period** will be contacted by telephone every 3 months ± 14 days to assess for survival status. Updated survival status may be requested by the Sponsor at any time during the study. Survival Phone Call Follow up will continue until death, participant request to discontinue from follow-up, or cut-off date for final analysis has been reached, or upon cancellation of Survival follow-up at the discretion of the Sponsor at any prior timepoint.

After the cohort cut-off date for the primary analysis, participants can continue to receive IMP, if clinical benefit is observed, until full permanent discontinuation criteria described in [Section 7](#) are met and will continue to undergo all assessments as per the study schedule of activities in the individual substudy.

For each cohort, the cut-off date for the final analysis (ie, analysis of secondary objectives and update of the primary objective) will be 3 years from cohort last participant in (LPI).

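### The E/S action in the mTPI2 rules names 24 µg/kg although the rules are reused at a reduced dose, and Cohort A's neutropenic-fever DLT omits grades above 3 (minor wording faults)

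*Protocol*

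**What the plan says.** **Dose rules (master protocol 4.1).** The run-in starts at 24 µg/kg and uses mTPI2. If the Study Board recommends it, the dose may be lowered to a level "which will be explored following the same process described in the safety run-in for 24" µg/kg.

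Two bullets turn the Table 2 code into an action:

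- On E or S, "all cohorts treated at the current regimen will continue with the SAR444245 24" µg/kg dose.
- On D or DU, "a dose lower than 24" µg/kg "will be tested and assessed with the same methodology". Inside this bullet, brackets define both codes as a move to the previous lower dose. DU adds that the current dose is barred for the rest of the trial.

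The bullets apply "unless decided otherwise by the Study Board", and the choice is introduced with the words "The dose decision (stay at 24" µg/kg, the alternative being to reduce. The Table 2 key names no dose: "E: Escalate to the next higher dose, S: Stay at the current dose", and for DU, "De-escalate to the previous lower dose and the current dose will never be used again because of unacceptable high toxicity".

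**DLT definition.** The master list (section 4.1) counts Grade 4 neutropenic fever with a temperature of at least 38.5 °C on more than one occasion. Substudy 01 section 4.1 adds, for Cohort A, Grade 3 neutropenic fever: neutrophils below 1000/mm³ with one reading above 38.3 °C, or above 38 °C for over an hour. It does not say that higher grades count.

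**The concern.** Bullet 1 is correct only while the dose being evaluated is 24 µg/kg. Once a lower dose is under test, a favourable result (E or S) read literally sends the cohort to 24 µg/kg. That disagrees with the Table 2 key on S. If 24 µg/kg was left because of a DU, it also names a dose that bullet 2 and the key rule out. Bullet 2 has the same anchor in looser form, because any reduced dose is already below 24 µg/kg.

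On the DLT list, the Cohort A line sets the lower fever threshold but attaches it to Grade 3 alone. A more severe event can therefore fall outside the line that counts the milder one.

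At stake are the written default for dose decisions in the run-in and one of the inputs to it.

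**Working it through.** **1. Table 2 itself.** With a Beta(1 + x, 1 + n − x) posterior, the intervals listed in section 4.1, and DU when Pr(rate > 0.3) exceeds 0.95, all 65 cells of Table 2 reproduce. The uniform prior and the 0.95 cutoff are conventional values assumed here; the documents do not state them. The table is sound, so the fault lies only in the action text.

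At n = 6: 0–1 DLT is E, 2 is S, 3 is D, 4 or more is DU. At n = 10: 0–2 is E, 3 is S, 4–5 is D, 6 or more is DU.

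**2. A path to the conflict.** Suppose 4 of 6 have a DLT at 24 µg/kg: DU, so the dose is barred. Then 1 of 6 has a DLT at the reduced dose: E. Bullet 1 read literally says to continue at 24 µg/kg, which the DU rule forbids.

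**3. Chance of reaching a reduced dose.** P(D or DU at 24) = P(X ≥ 3) for X ~ Bin(6, p), or P(X ≥ 4) for X ~ Bin(10, p). For n = 6 and p = 0.30: 1 − (0.1176 + 0.3025 + 0.3241) = 0.256.

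| True DLT rate at 24 µg/kg | n = 6 | n = 10 |
|---|---|---|
| 1/6 | 0.062 | 0.070 |
| 30% (the mTPI2 target) | 0.256 | 0.350 |
| 40% | 0.456 | 0.618 |

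The 1/6 row matches master protocol 4.3, which reports 1 DLT among 6 treated with 24 µg/kg plus pembrolizumab, and bears on Cohort A. For Cohort C1 the nearest data are monotherapy every 3 weeks, while C1 doses every 2 weeks. There, 11 were treated at 24 µg/kg and the only monotherapy DLT was at 32 µg/kg. If all 11 were evaluable, the one-sided 95% upper bound is 1 − 0.05^(1/11) = 23.8%, and P(X ≥ 3 | 6, 0.238) = 0.152.

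**4. Chance of then meeting bullet 1 at the reduced dose.** Take 30% at 24 µg/kg and an assumed 5% to 25% at the reduced dose.

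- n = 6: P(E or S) at the reduced dose is 0.9978 to 0.8306. Joint: 0.2557 × 0.9978 = 0.255, down to 0.2557 × 0.8306 = 0.212.
- n = 10: P(E or S) is 0.9990 to 0.7759. Joint: 0.3504 × 0.9990 = 0.350, down to 0.3504 × 0.7759 = 0.272.
- DU at 24 µg/kg followed by E or S, the direct contradiction: 0.0705 × 0.9978 = 0.070, down to 0.0705 × 0.8306 = 0.059 (n = 6); 0.047 down to 0.037 (n = 10).

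**5. The two fever lines side by side.** Take neutropenic fever with neutrophils below 1000/mm³ and a single reading of 38.4 °C.

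| Event | Cohort A line (Grade 3; one reading > 38.3 °C) | Master line (Grade 4; ≥ 38.5 °C more than once) | DLT by a fever line? |
|---|---|---|---|
| Grade 3 | met | not met | yes |
| Grade 4 | not met (grade) | not met (temperature) | no |

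Other master lines would catch the Grade 4 event only if it came with Grade 3 or above hypotension or cytokine release syndrome. The line on Grade 3 or above events not resolving within 7 days might catch it if prolonged, though that line is listed under non-hematologic events. At n = 6 or 10, one uncounted DLT changes keep-versus-reduce only at a boundary: 3/6 (D) read as 2/6 (S), or 4/10 (D) read as 3/10 (S).

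**The case against.** The strongest reply is that nobody would apply bullet 1 literally below 24 µg/kg. A cohort on a lower dose cannot continue with 24. The Study Board paragraph in 4.1 and section 9.5 offer only confirmation or reduction, cohorts fill at whichever dose is confirmed as safe, the Table 2 key is dose-neutral, and the Board may override. All of this stands. It makes the intent clear and keeps the point minor. It does not make the written default correct for the reuse that the section announces.

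Three stronger readings are tempting and are not supported:

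- *After D or DU at a reduced dose, bullet 2 would allow that dose to stay.* The bullet's own definitions of D and DU require a move below the current dose, and it already carries the DU bar. Its anchor is loose, but the instruction is not lost.
- *The plan leaves open a return to 24 µg/kg after a favourable reduced dose.* The Board's stated choices contain no escalation, and even E at 24 µg/kg means only continue.
- *Grade 4 neutropenic fever is not a DLT in Cohort A.* Substudy 01 adds to the master list, so the Grade 4 line applies. Only the temperature gap shown in the working remains.

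The lower Cohort A threshold is a legitimate cohort-specific choice and is not criticised.

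**Conclusion.** Both faults are real and minor. Bullet 1 conflicts with the Table 2 key at any reduced dose, and with the DU bar if 24 µg/kg returned DU. The Cohort A fever line can count a Grade 3 event and miss the Grade 4 event with the same reading.

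A reader might take the probabilities as chances of a wrong dose. They are not: they are chances of arriving at a step for which the sentence was not written, under assumed DLT rates. Nothing in the documents suggests that a Study Board would act on the literal words. For the fever gap the documents give no event frequency, so no likelihood is claimed. The Board's overall safety assessment and its power to stop a cohort for too many Grade 4 or 5 events limit the harm further.

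The conclusion does not depend on the blacked-out reduced dose. Figure 1 of the protocol is not visible and may show a reduced-dose branch. That would support the inferred intent but would not alter the wording of the bullet.

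**What to change.** In master protocol 4.1, replace 24 µg/kg in both action bullets with *the dose under evaluation*: on E or S, cohorts continue at that dose; on D or DU, a dose lower than it is tested by the same method. No extra sentence on DU is needed, because bullet 2 and the Table 2 key already contain the bar.

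In Substudy 01 section 4.1, write *Grade 3 or above neutropenic fever* and leave the neutrophil and temperature thresholds as they are.

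The cost is a few words in each bullet and two words in the substudy. Table 2, the sample size and the endpoints are unaffected.
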